#### 3.2.2 Outcome measures

Primary outcome measure: Crude mortality at 30 days and 6 months after the sample was taken will be compared between case and controls, those that received a correct diagnosis at the original hospital and those that were 'missed' (either due to lack of testing or inadequate testing) and between community and hospitalised patients.

Secondary outcome measures: Patient length of stay, severity of infection (e.g. WCC, serum albumin, temperature), need for escalation of medical/surgical care due to gastrointestinal disease, post-infectious sequelae.

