#### 3.2.6 Data collection

Data will be collected via a standardised CRF, with a full supporting SOP. The CRF will be completed by the clinical care team at the participating site that submitted the sample (during O1.1). The CRF will not contain any participant identifiable data; all data will be held against a pseudoanonymised study code, with the link back held by the clinical care team only. COMBACTE-CDI investigators will not access participant's notes or access the link back. Once the CRF data has been collected and validated and verified the link-back will be destroyed by the local study site.

Data will be collected on the following variables on outcomes of CDI;

- Evidence of other enteric pathogens (+/- 7 days of the original sample)?
- Symptoms at time of the sample
- Alternative cause for the patient's diarrhoea documented (e.g. laxatives, pathogen)?
- Duration of diarrhoea/non-normal bowel habit?
- Primary/recurrent CDI
- Antibiotics at the time of the sample or the preceding 3 months?
- Evidence of colitis?
- Evidence of post-infectious diarrhoea

- CDI Severity markers (Temperature (nearest reading +/- 3 days of the sample), serum creatinine (nearest reading +/- 3 days of the sample), White cell count (nearest test +/- 3 days of the sample)
- Treatment for CDI episode
- Was treatment for CDI/diarrhoea escalated medical/surgical?
- Outcome 30 days and 6 months after the sample (discharged, in-patient, died)
- Length of stay

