This enriched case/control study will provide data on the difference in severity of CDI and the risks and outcomes for these different 'diagnostic types'. There are a paucity of data on these differences, particularly with regard to the new technology of the SIMOA assay. A retrospective CDI case-control study is proposed to determine the outcomes and risk factors for CDI, but different diagnostic criteria, for patients both within the hospital setting and in the community.

Ethical and regulatory approvals are in place for each site within the case/control study, as per the COMBACTE-CDI full study protocol.

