## 2.1 Selection of case and controls (total possible to be recruited)

		Location	of participant a sample	at time of
Diagnostic categories:		Hospital	Community	TOTAL
CDI positive cases	1. CCNA positive	83	20	103
	2. CCNA negative/Simoa positive	49	22	71
	3. CCNA and Simoa negative but CTC positive or bioFire pos	24	15	39
CDI negative controls	4. Negative control *	365	147	512
Total number selected for case/control study 521 204		725		

Table1. The total number of samples selected for the case/control study (n=725). The table shows the number of CDI positive cases according to the indicated diagnostic categories (1-3, n=213) and by location of participant (Hospital n=156, Community n=57). Negative controls (4, n=512) were selected at a rate of 1:3 from matching participating sites (one case to three controls). As some participating sites had less than 3 controls per case, average rate was of 1:2.4 (one case to 2.4 controls) (\*).

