#### 4. Study Design

This is case-control study with the cases and controls selected from the patients who had stool samples tested for CDI. The study will collect data on cases/controls (1:3 ratio) identified during the sample collection phase of COMBACTE-CDI.

For each case of confirmed CDI (or other diagnostic criteria), three controls will be randomly selected from the same participating site (i.e. if hospital case, controls will come from the same hospital, if community case, controls will come from the community). Thus initially the controls are only matched on location only, as the cohort is not large enough to enable closer matching. Subsequent further matching (e.g. by age) may be considered depending on final available sample size, but this would reduce the overall pool of controls substantially.

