#### 7.2 Univariate analysis

Univariate analysis will be used to assess outcomes and risk factors; continuous variables will be compared between cases and controls by t-test; categorical variables will be compared between cases and controls by chi-squared (fishers exact where numbers are below 5). Risk ratios (Odds ratio if it is case control study) will be calculated for CDI cases with identified variables of interest. Univariate analysis will be used to assess consistency between countries and between different healthcare settings.

The variables to be included in the univariate analysis are shown in the table in appendix 1.

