#### 7.3 Regression analysis (or Multivariate analysis)

To evaluate risk factors considering confounding, unconditional logistic regression analysis will be perform with case/control as dependent variable, and all variables listed in the univariate analysis as independent variables.

To build the logistic regression model, we will apply a stepwise forward selection to identity risk factors. The process of the forward selection will be recorded to rank the risk factor.

The regression analysis will be performed separately for the three age groups (18-49,50-64 and 65+ years). If there is a reasonable sample size analysis will also be performed for the age group <18 years.

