	CDI graded?			when the sample
				was taken
4.5.1	If yes, please record	Categorical	Univariate/multivariate	Patient admission
	the severity of CDI			when the sample
				was taken
4.6	Has the patient	Binary	Univariate	Patient admission
	ever had CDI			when the sample
E Clinica	Information			was taken
5.1	Temperature	Continuous	Univariate	Patient admission
5.1	(highest reading +/-	Continuous		when the sample
	3 days of the index			was taken
	sample)			
5.2	Serum creatinine	Continuous	Univariate	Patient admission
	(highest reading +/-			when the sample
	3 days of the index			was taken
	sample)			
5.3	White cell count	Continuous	Univariate	Patient admission

	(highest +/-3 days			when the sample
	of the index			was taken
	sample)			
5.4	Serum Albumin	Continuous	Univariate	Patient admission
	(lowest +/-3 days of			when the sample
	the index sample)			was taken
5.5	Primary diagnoses	Categorical	Univariate	Patient admission
	at time of index			when the sample
	sample			was taken
5.6	Does the patient	Binary	Univariate	Patient admission
	have any significant			when the sample
	illnesses			was taken
5.6.1	If yes, are the	Categorical	Univariate	Patient admission
	illnesses:			when the sample
				was taken
	Acute/chronic			
5.6.2	Please provide	Categorical	Univariate	Patient admission
	details of the			when the sample
	significant illness			was taken
5.7	Co-morbidities		All of these could be	
			Covariates	
	Myocardial	Binary	Univariate/multivariate	Patient admission
	infarction			when the sample
				was taken
	Congestive heart	Binary	Univariate/multivariate	Patient admission
	failure			when the sample
	De debe velo e e de c	D'		was taken
	Peripheral vascular	Binary	Univariate/multivariate	Patient admission
	uisease			when the sample
	Corobrovascular	Pipany	Univariato (multivariato	Rationt admission
	disease	Billary	Onivariate/multivariate	when the sample
	uiscase			was taken
	Dementia	Binary	Univariate/multivariate	Patient admission
	Dementia	Dinary		when the sample
				was taken
	COPD	Binary	Univariate/multivariate	Patient admission
		,	,	when the sample
				was taken
	Peptic Ulcer disease	Binary	Univariate/multivariate	Patient admission
				when the sample
				was taken
	Cystic fibrosis	Binary	Univariate/multivariate	Patient admission
				when the sample
				was taken
	Diabetes without	Binary	Univariate/multivariate	Patient admission
	organ damage			when the sample

			was taken
Leukaemia within	Binary	Univariate/multivariate	Patient admission

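### Temperature, creatinine, white cell count and albumin are compared by unadjusted t-test with no adjusted difference planned, so age and pre-existing disease may explain part of any case–control gap.

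*SAP*

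**What the plan says.** Protocol 3.2.2 lists among the secondary outcomes "severity of infection (e.g. WCC, serum albumin, temperature". Protocol 3.2.6 groups the items to be collected under "CDI Severity markers (Temperature (nearest reading +/- 3 days of the sample), serum creatinine" and white cell count. SAP section 1 states that the study "will provide data on the difference in severity of CDI and the risks and outcomes for these different" diagnostic types, and SAP 2.5 sets out to compare outcomes of each case classification with controls.

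The analysis of these markers is in three places:

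- **SAP 7.2:** univariate analysis is used to assess outcomes and risk factors, and "continuous variables will be compared between cases and controls by t-test".
- **SAP Appendix 1, items 5.1–5.4:** temperature, creatinine, white cell count and "Serum Albumin" are tagged for univariate analysis only. Age, gender, location and the listed comorbidities are tagged for both univariate and multivariate analysis.
- **SAP 7.3:** the only regression has case/control status as the dependent variable. It uses forward selection by age group and takes "all variables listed in the univariate analysis as independent variables".

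On matching, SAP 4 says: "Thus initially the controls are only matched on location only, as the cohort is not large enough to enable closer matching". Age matching may be considered later.

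**The concern.** A t-test on creatinine or albumin attributes the whole group difference to case status. These markers can also vary with age and with kidney, liver or haematological disease. The protocol's age and gender matching (3.2.3, softened to where possible in 3.2.5) has become matching on location only. The SAP's own planning figures show cases older than controls. SAP 7.3 is justified by the need to consider confounding for risk factors; no counterpart is written for severity.

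SAP 7.3 and the Appendix also disagree. The Appendix tags keep items 5.1–5.4 out of the multivariate model, while the wording of 7.3 brings them in. Neither reading yields an adjusted difference in a marker, whether between a case type and controls or between two case types. At stake is whether a reported severity difference can be read as a feature of CDI or of its diagnostic type, and not of who the patients were.

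**Working it through.** The documents give no SD, expected difference or power for any marker, so there is no planned figure to reproduce. The check is an illustration of confounding in the raw t-test.

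**Inputs from the documents**

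- SAP 2.1, Table 1: 103 CCNA-positive, 71 Simoa-only and 39 culture/gene-only cases (103 + 71 + 39 = 213), and 512 controls.
- Hospital patients: 83/103 = 80.6%, 49/71 = 69.0%, 24/39 = 61.5%; all cases 156/213 = 73.2%; controls 365/512 = 71.3%.
- SAP 3: over 65, 65% of cases and 39% of controls in an earlier study, a gap of 0.26. The same paragraph quotes a detectable difference of 23%; the two proportions differ by 26 points.

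**Assumptions:** the marker differs by D = 0.2 to 0.5 SD between over- and under-65s; CDI has no true effect; the test is two-sided at 5%.

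**Formulas (SD units):** bias = gap × D; SE = √(1/n₁ + 1/n₂); rejection probability = Φ(−1.96 + bias/SE) + Φ(−1.96 − bias/SE).

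**Age**

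| Comparison | SE | Bias | Rejection at D = 0.2, 0.3, 0.4, 0.5 |
|---|---|---|---|
| 213 v 512, gap 0.26 | 0.0815 | 0.052–0.130 | 9.8%, 16.0%, 24.7%, 35.8% |
| 103 CCNA-positive v 512, gap 0.26 | 0.1080 | 0.052–0.130 | 7.7%, 11.2%, 16.1%, 22.6% |
| 128 v 307 (60% have a result, assumed), gap 0.26 | 0.1052 | 0.052–0.130 | 7.8%, 11.5%, 16.7%, 23.5% |
| 213 v 512, half the gap (0.13) | 0.0815 | 0.026–0.065 | 6.2%, 7.7%, 9.8%, 12.5% |

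In a simulation of 8,000 studies (213 v 512, the 65% v 39% split, no CDI effect), raw v age-adjusted rejection was 9.9% v 4.9% at D = 0.2 and 34.3% v 5.0% at D = 0.5. The SE rose from 0.0819 to 0.0840 (about 3%) and from 0.0838 to 0.0839 respectively. Only age was adjusted for.

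**Care setting** (assumed setting effect 0.2–0.5 SD)

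- All cases v controls: gap 0.732 − 0.713 = 0.020, bias 0.004–0.010 SD, rejection 5.0–5.2%.
- CCNA-positive v all 512 controls: gap 0.093, rejection 5.3–7.1%.
- Between case types: CCNA-positive v Simoa-only, gap 0.116, 5.3–6.6%; CCNA-positive v culture/gene-only, gap 0.190, 5.5–8.0%; Simoa-only v culture/gene-only, gap 0.075, 5.1–5.4%.

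**Precision between case types:** the 95% CI half-widths (1.96 × SE) are 0.30, 0.37 and 0.39 SD for the same three pairs, even if every patient has a result.

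**The case against.** The strongest reply is that SAP 7.3, taken literally, already covers the point. It enters every univariate variable, and therefore the markers, in models run by age band with age and comorbidities as candidates. The Appendix says the comorbidities could be covariates. A marker's coefficient would then test its association with case status given the covariates retained. This stands in part: on that reading confounding is partly handled, and the age-based error rates above do not apply. It does not supply the missing quantity. The output is an odds ratio of being a case, available only if stepwise selection keeps the marker. There is no adjusted difference and no contrast between diagnostic types.

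Other points on that side that stand:

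- A reader might infer that controls are unbalanced on location for each case type. SAP 4 selects controls for each case from the same site and setting, and SAP 2.1 says they "were selected at a rate of 1:3 from matching participating sites". The hospital-share gaps v controls matter only if each type is compared with all 512, which the SAP does not say.
- A reader might infer that 10–36% applies to contrasts between diagnostic types. It does not: the documents give no age gap between types.
- Protocol 3.5.1 notes that albumin may be a cause or an effect of severe CDI, so it is too strong to say that all four markers are purely consequences of CDI.
- Locally graded severity (item 4.5.1) is tagged for multivariate analysis. That is a separate item, recorded only where CDI was graded, and gives no adjusted marker difference.
- These are secondary outcomes. Mortality, the primary outcome of objective 1.3, has no outcome model either; this point is confined to items 5.1–5.4.

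The age stratification in SAP 7.1 does not answer the point, because it concerns descriptive tables and not the 7.2 tests.

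**Conclusion.** The concern holds as a gap in the analysis of a stated secondary outcome. The only specified comparison of the four markers is a raw t-test, the groups are unmatched on age and chronic disease, and no model has a marker as its outcome.

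For pooled cases v controls under the raw t-test, the spurious difference is 0.05–0.13 SD. The false-positive rate is 10–36% with full testing, about 8–24% if 60% have results, and 6–13% with half the age gap and full testing. These figures rest on one earlier study's age split and an assumed 0.2–0.5 SD age effect, so they show plausible size and are not a prediction.

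Two stronger readings are not supported. One is that the plan ignores confounding altogether; 7.3 read literally handles some of it. The other is that care setting drives the differences; it is negligible for pooled cases (73% v 71% hospital) and small by type. The change should be made, but it does not threaten the study as a whole.

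**What to change.** In SAP 7.2 and Appendix 1 items 5.1–5.4, specify for each marker a linear regression on diagnostic category (three case types and control), with creatinine and white cell count on the log scale. Adjust for age, sex and hospital/community location, and for the relevant pre-existing condition:

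- chronic kidney disease for creatinine;
- leukaemia or lymphoma, and chemotherapy in the preceding 12 weeks, for white cell count;
- liver disease for albumin.

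Account for country or site as numbers allow; the form (fixed effects or a random intercept) is a matter of preference. Report adjusted differences with 95% CIs for each case type v controls and between case types, and keep raw means as descriptive.

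Resolve the conflict between 7.3 and the Appendix by following the Appendix tags, stating that items 5.1–5.4 are not candidate predictors in the risk-factor model.

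The cost is SAP wording and four regressions on items already collected. Patients with a missing covariate are lost and some precision is given up. The 0–3% increase in SE was shown for age adjustment only; the fuller model was not tested, and one case type has only 39 patients. Adjustment will not remove bias from selective blood testing.

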Appendix 1. Variable description table

## 1. Introduction

This statistical analysis plan (SAP) is to provide a description of the study design, study variables, and statistical analysis methods for the COMBACTE-CDI study, which aims to develop a detailed understanding of the epidemiology and clinical impact of CDI. More specifically, this project's objectives are to:

- Align and understand the unmet public health needs relating to CDI;
- Identify and quantify the direct and long-term burden of CDI on healthcare systems

The COMBACTE CDI case/control studyfollows a cohort of patients identified during the COMBACTE CDI sample collection study. The sample collection study involved 119 sites from 12 countries from Europe, with a national coordinator recruited for every country. National coordinators selected participating sites (PS) to cover all major geographical regions within every country. Participating sites were recruited at a rate of one per 3 million population in all study countries. Figure 1 shows the full study design.

Figure 1. Schematic representation of study design (WP1 &WP2). A synergistic approach will enable completion of all the objectives from WP1 and WP2, with data created from a single, large complex study flowing into other objectives for further results analysis. Boxes in blue denote objectives in WP1, and those in orange denote for objectives in WP2. Due to the inter-related nature of the

objectives within both WP1 and WP2, the flow of work has been planned to ensure maximum outputs within the timeframe of the grant. The directions of the arrows indicates data flow and, therefore, also the timing of activities; i.e. Strains cannot be analysed (1.2) until after they have been collected (1.1). This ambitious comprehensive project design takes influence from several existing, separate studies; the scope of producing all of these is data from one, well-designed and far-reaching study is novel and innovative.

During the COMBACTE-CDI sample collection study, cases and controls were identified; Multiple diagnostic definitions of a case;

- Case defined as C. difficile toxin positive (gold standard method CCNA) positive
- Case defined as C. difficile toxin positive (new novel method –SIMOA)
- Case defined as free toxin negative but positive for a cytotoxigenic strain (by culture or detection of toxin gene)
- Control defined as negative by all assays

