#### 2.5. Analysis objectives

The main objectives of the analyses are to;

- 1. Determine the outcomes of cases (of each classification) vs controls, and compare between countries and hospital vs community cases
- 2. Determine the risk factors for cases (of each classification) vs controls, and compare between countries and hospital vs community cases

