## 6.3. Study period and important time points.

The study period is June 2018-June 2019.

The index date for the cases is defined as the date of the stool sample collection (either June/July 2018 or Oct/Nov 2019).

The index date for the controls is defined as the date of the stool sample collection either June/July 2018 or Oct/Nov 2019).

Queries within the CRF relate to that patients episode, with reference to the six months prior and six months subsequent to the index sample.

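### SAP 7.2 picks the effect measure by study label, so forward-followed outcomes would naturally get odds ratios, and no risk difference with an interval is specified

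*SAP*

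**What the plan says.** SAP 2.5 has two objectives. The first is to "Determine the outcomes of cases (of each classification) vs controls"; the second is to determine risk factors. SAP 7.2 covers both at once: "Univariate analysis will be used to assess outcomes and risk factors". Its effect-measure rule is "Risk ratios (Odds ratio if it is case control study) will be calculated". The condition in the parenthesis is the type of study, not the direction of the comparison.

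SAP 4 settles the type: "This is case-control study with the cases and controls selected from the patients who had stool samples tested for CDI". SAP 1, however, says the case/control study follows "a cohort of patients identified during the COMBACTE CDI sample collection study", and SAP 6.3 has the CRF questions asked "with reference to the six months prior and six months subsequent to the index sample".

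Protocol 3.2.2 makes crude mortality at 30 days and 6 months the primary outcome for objective 1.3. SAP Appendix 1 section 10 lists discharge, admission and death after the sample. Protocol 3.2.7 says crude and attributable mortality rates will be compared between settings and countries. SAP 7.1 plans numbers and percentages for categorical variables. The only regression, in SAP 7.3, is a logistic model with case/control status as the dependent variable.

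**The concern.** Odds ratios are needed when sampling depends on the outcome being compared, because group risks then cannot be recovered. That describes objective 2, where CDI status is the outcome and earlier exposures are compared. In objective 1 CDI status is the exposure, and death, discharge and admission come later. Sampling did not depend on them, so the usual reason for the odds ratio is absent.

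The study's stated aim is to quantify the burden of CDI. Burden is most directly expressed as excess deaths or admissions per patient, which an odds ratio alone does not give. For a common outcome, a reader may also take the odds ratio for a risk ratio and so overstate the effect.

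SAP 7.3 does not fill the gap. Case/control status is its dependent variable, and Appendix 1 marks the section 10 outcomes for multivariate as well as univariate analysis. Read literally, later deaths and admissions could enter as predictors of CDI status. No model has an outcome as the dependent variable.

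**Working it through.** **The plan's own figure.** SAP Table 1 has 103 + 71 + 39 = 213 cases and 512 controls, 725 in all. 512/213 = 2.40, which agrees with the stated average of 1:2.4. Selection was on CDI status and site, not on later outcomes.

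**Formulas.** With risk p1 in cases and p0 in controls: RR = p1/p0, RD = p1 − p0, OR = [p1/(1 − p1)]/[p0/(1 − p0)].

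**Assumed inputs.** Neither document gives an outcome risk, so p0 is varied from 2% to 50% with the true RR held at 1.5. The last column is (OR − 1)/(RR − 1) − 1, the overstatement if the OR is read as an RR.

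| p0 | p1 | RR | OR | RD (points) | Relative excess overstated by |
|---|---|---|---|---|---|
| 2% | 3% | 1.50 | 1.52 | 1 | 3% |
| 5% | 7.5% | 1.50 | 1.54 | 2.5 | 8% |
| 10% | 15% | 1.50 | 1.59 | 5 | 18% |
| 20% | 30% | 1.50 | 1.71 | 10 | 43% |
| 30% | 45% | 1.50 | 1.91 | 15 | 82% |
| 40% | 60% | 1.50 | 2.25 | 20 | 150% |
| 50% | 75% | 1.50 | 3.00 | 25 | 300% |

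Example at 30%: (0.45/0.55)/(0.30/0.70) = 0.818/0.429 = 1.91.

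The gap also appears below 1. Discharge within 30 days of 70% in cases against 80% in controls (assumed) gives OR (0.70/0.30)/(0.80/0.20) = 0.58, against RR 0.70/0.80 = 0.88.

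**What the study size could report.** Wald 95% intervals at 213 and 512, ignoring site, for assumed risks:

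- 45% v 30%: RD 15.0 points (7.2 to 22.8), RR 1.50 (1.23 to 1.83), OR 1.91 (1.37 to 2.65).
- 10% v 5%: RD 5.0 points (0.6 to 9.4), RR 2.00 (1.15 to 3.47), OR 2.11 (1.16 to 3.84).

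For the first RD, SE = √(0.45×0.55/213 + 0.30×0.70/512) = 0.0397, and 1.96 × 0.0397 = 0.078.

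**Smallest cells.** In Table 1 the three community case classes have 20, 22 and 15 cases, and the third hospital class has 24. For 15 cases against 147 community controls at an assumed 25% v 15%, SE = √(0.25×0.75/15 + 0.15×0.85/147) = 0.116, so the interval is about ±23 points.

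**The case against.** **The rule may already permit this.** SAP 7.2 names the risk ratio first and the odds ratio only as the case-control exception, and SAP 1 describes a cohort that is followed. Applied analysis by analysis, the rule would give risk ratios for outcomes. This stands in part: the text is ambiguous. But SAP 4 labels the whole study case-control, and nothing in SAP 7.2 separates the two objectives.

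**The odds ratio is valid under either direction of sampling.** This stands. A reader might infer that the planned outcome analysis is wrong, or that its effects will generally look much larger than the risk ratio. The documents do not support either inference. They give no outcome risks, and if 30-day mortality is below about 10%, the two measures are close.

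**Absolute information is partly planned.** This also stands. SAP 7.1 gives percentages, although its list of items tabulated by case and control does not name outcomes. Protocol 3.2.7 intends attributable mortality, and Appendix 1 items 10.5.1 and 10.7.1 record whether a death was linked to CDI. It would therefore be too strong to say that no absolute information is planned. What is missing is a difference with an interval and a definition of the attributable part; a linked-death flag is not a case-minus-control excess.

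**The cost work does not depend on this table.** Protocol 3.6.6 sends the combined data to the modelling partner, who can derive risks from them. That removes any claim that the cost work is blocked. It does not supply the clinical report with an excess risk.

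**A crude pooled difference would mislead too.** This stands and shapes the fix. Controls were drawn within site at varying ratios and are not age-matched (SAP 2.1 and 4). SAP 4.1.5 also removes controls with a CDI-positive sample up to 8 weeks after the index date, which conditions on follow-up.

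**Conclusion.** The point holds as a minor, nearly free improvement. On the natural reading of SAP 7.2 with SAP 4, outcomes receive odds ratios because of the study label, although their risks are estimable, and no estimator of excess risk is specified.

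The practical size depends on outcome frequency. With a true risk ratio of 1.5, the odds ratio exceeds it by 0.09 or less at control risks up to 10%, by 0.41 at 30%, and is twice as large at 50%. These figures rest on assumed risks. Whether discharge, admission or 6-month death is common enough to matter cannot be settled from the documents. The missing risk difference matters at any frequency, because the objective is burden.

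No wrong test result follows from the present wording. The issue is interpretability and fit to the objective. Nor would a risk difference by itself be attributable burden: that reading also needs control of confounding, since controls are not matched on age.

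**What to change.** In SAP 7.2, separate the two objectives.

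- For risk factors that precede the sample, keep odds ratios.
- For post-sample outcomes (Appendix 1 section 10, including 30-day and 6-month mortality), report the risk in each group, the risk difference and the risk ratio with 95% intervals. Six-month mortality combines items 10.5 and 10.7, because 10.7 covers only deaths after day 30.
- Take these estimates from an analysis with the outcome as dependent variable and CDI class as exposure, accounting for site and setting. Mantel–Haenszel estimates stratified by site and setting, or standardised risks from a logistic model, would serve.
- In SAP 7.3, state that post-sample outcomes are not candidate predictors of case status.
- Show the result with and without the exclusion of controls who had a CDI-positive sample in the 8 weeks after the index sample.
- State how the attributable mortality of Protocol 3.2.7 is estimated, or drop the term.

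The data and software are unchanged. The cost is a few sentences in the SAP, slightly more analysis, and wide intervals in the class-by-setting cells of 15 to 24 cases, which should be labelled descriptive.
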